#### Document Version History

Version Number	Approval Date	Description of Change
V1.0	13 August 2024	N/A
V2.0	13 August 2024	Clarifying language per human ethics committee review request. No fundamental protocol amendments.

### 3 Study Synopsis

RMI Oceania (the legal manufacturer and sponsor) has developed an ultrasound imaging Robotic Ultrasound Assistance Tool ‘RUAT’ that has the capacity to provide robotic systems which can be integrated into a healthcare system’s specific digital network. This robot functions as a collaborative ‘ROBOT’ or ‘COBOT’ where a human operator remote controls the arm for image acquisition. The RUAT can be deployed in any location (including regional and remote) and controlled remotely with the sonographer using a novel workstation-based control system.

This is a pilot “Safety and Useability” Clinical Investigation of the RUAT system to perform an echocardiographic examination.

Up to 30 participants (over a 2-month period) will be recruited from inpatients and outpatients of the Royal Brisbane and Women’s Hospital who have already received a standard (manual) echocardiogram examination and deemed suitable based on willingness to undergo the RUAT Echo scan for research purposes and are able to consent and participate.

The primary objectives include to:

- a. assess the **safety** of the RUAT echo.
- b. assess the **useability (functionality)** of using the RUAT echo as intended to obtain echocardiogram images of clinically suitable quality for reporting by a cardiac sonographer.

	QMS Template	Doc ID: RMI-ROBOTECHO-CIP-002 Ver No: V2.0
	Clinical Investigation Protocol	

#### 4 Schedule of Assessments

Procedure	Visit Structure		
	Screening	Day of RUAT Echo	Safety Follow-up visit /End of Study  72 hours post scan
Manual echo (prior to RUAT study) 	X		
Informed consent	X		
Review inclusion and exclusion criteria 	X		
Demographics	X		
Echocardiogram using RUAT ECHO		X	
Functional verification of RUAT ECHO		X	
Participant experience Surveys 		X	
Adverse events/Adverse device events	Continuous from informed consent signature to end of study		

 Safety Follow-up visit may be conducted by telephone call or onsite if inpatient, within 72 hours after the examination.

 As part of the selection criteria participant will have recently undergone a manually performed echocardiogram. Any bruising or soreness will be documented as part of the screening and consent, ruling ineligible if the discomfort is too severe.

 Participants must have undergone a clinical (manual) echocardiogram performed and reported as per usual clinical pathway **prior** to study entry. All clinical decisions will be made based on this echocardiogram.

 Participant survey to be completed on paper after the RUAT Echo with the support of the observing sonographer.

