### 8.1 Length of Study

Participants will be recruited until 30 participants have been recruited, estimated time is approximately 3 months.

Participants will undergo a single RUAT ECHO, which takes approximately 30-60 minutes.

Participants will undergo a single safety follow-up contact up to 72 hours ~~18-24 hours~~ after the RUAT ECHO is performed, either in person if inpatient or by telephone call/telehealth if outpatient/discharged patient.

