### 10.3.2 Time Period and Frequency for Collecting AE, ADE, SAE and SADE Information

All AEs, ADEs, SAE and SADEs will be collected from the signing of the patient informed consent form (PICF) until 72 hours post RUAT Echo, i.e., end of the study.

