### 10.3.3 Method of Detecting AEs and SAEs

Care will be taken not to introduce bias when detecting AEs, ADEs, SAEs and/or SADEs. Open-ended and nonleading verbal questioning of the participant is the preferred method to inquire about AE/ADE occurrences.

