### 10.3.4 Classification System

Investigators will be asked to assess the potential relationship of the adverse event to the ROBOT ECHO and/or to the procedure. For this study, each AE/ADE will be classified as device- or procedure-related. The following definitions will be used:

- **Procedure-related:** An adverse event that occurs due to the system application procedure. Commonly experienced events from an Echocardiogram include potential bruising, discomfort, focused pressure from the probe, lubricating gel may feel cold.
- **Device Related:** An adverse event that results from the presence or performance of the device or any other component of the system, for example if the RUAT robotic arm pushes too hard on the patient and fractures a rib.
- **Unknown:** If the adverse event cannot be determined to have a causal relationship with either the device or procedure, it will be classified as unknown.

The severity or intensity of each AE/ADE will be classified as per the below definitions:

- **Mild:** Patient is aware of event or symptom, but event/symptom is easily tolerated.
- **Moderate:** Patient experiences sufficient discomfort to interfere with or reduce their usual level of activity.
- **Severe:** Significant impairment of functioning; patient is unable to carry out usual activities.

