#### 11.1.1 Decision Criteria

The primary objectives of the study are to:

- assess the **safety** of the RUAT echo.
- assess the **“useability” (functionality)** of using the RUAT echo as intended to obtain echocardiogram images of clinically suitable quality for reporting by a cardiac sonographer.

The **safety** of the RUAT Echo will be considered acceptable if there are no device related adverse effects.

RUAT Echo will be considered a **useable** method of performing echocardiograms if:

- Each functional verification criteria 1 through 11 (inclusive) performed “YES” at least 80% of the time an echocardiogram was performed by RUAT Echo, that is, pass functional verification (see APPENDIX 1 - Functional Verification ).
- At least 80% of echocardiograms performed by RUAT Echo are considered of an adequate quality to provide a diagnostic assessment, that is, pass functional verification item #12 (see APPENDIX 1 - Functional Verification ).
- At least 80% of participants report they are satisfied with undergoing RUAT Echo examination based on an average of the 4 subscales of the 10-point Likert scales from strongly disagree to strongly agree (see APPENDIX 2 – Participant Survey).

	QMS Template	Doc ID: RMI-ROBOTECHO-CIP-002 Ver No: V2.0
	Clinical Investigation Protocol	

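### The only safety contact has a latest time but no earliest one, so a compliant early call ends scheduled questioning before the 72-hour adverse event window closes

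*Protocol*

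**What the plan says.** Four places in the protocol bear on the timing of safety follow-up.

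- **Section 4, column head.** The last visit is labelled "Safety Follow-up visit /End of Study" and timed at "72 hours post scan".
- **Section 4, footnote 1, attached to that head.** "Safety Follow-up visit may be conducted by telephone call or onsite if inpatient, within 72 hours after the examination".
- **Section 8.1.** "Participants will undergo a single safety follow-up contact up to 72 hours" after the scan, in person for inpatients and by telephone or telehealth for the others.
- **Section 10.3.2.** Events are collected from consent "until 72 hours post RUAT Echo, i.e., end of the study".

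On detection, Section 10.3.3 states: "Open-ended and nonleading verbal questioning of the participant is the preferred method to inquire about AE/ADE occurrences". After the single contact, the protocol schedules no second call, diary or record check.

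On the decision, Section 11.1.1 says that safety "will be considered acceptable if there are no device related adverse effects".

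**The concern.** The limit on the contact is on the wrong side. A contact that is meant to cover a 72-hour window has to take place at the end of that window or just after it. Footnote 1 and Section 8.1 instead allow any time up to 72 hours and nothing later. The column head, the footnote and Section 10.3.2 agree only if every call is made at 72 hours exactly. A call at 73 hours, which could ask about the whole window, would breach the footnote, and Section 10 allows no waivers.

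The end of collection is also unclear. Section 4 collects events until the end of the study and labels the contact as that end, whereas Section 10.3.2 puts the end at 72 hours. After a call at 24 hours, an event at 48 hours is inside the window under Section 10.3.2 but arguably after the end of the study under Section 4. The reading kinder to the plan is that the window stays open, and that reading is used below.

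What is at stake is a primary objective with a zero-event rule. One missed device-related effect can turn a fail into a pass, and incomplete capture cannot work in the other direction. Missing data are not imputed (Section 11.1.4) and no sensitivity analysis is planned (Section 11.3.2.2). In any case, no analysis can recover an event that nobody asked about.

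**Working it through.** The protocol gives no figure for this point, so there is none to reproduce. The check has two parts.

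**1. Timing**

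Inputs: the contact may take place at any time *t* with 0 < *t* ≤ 72 h (footnote 1, Section 8.1), and collection ends at 72 h (Section 10.3.2).

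Hours without scheduled questioning = 72 − *t*.

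| Contact at | Complies with footnote 1 | Hours not asked about |
|---|---|---|
| 2 h | yes | 72 − 2 = 70 |
| 24 h | yes | 72 − 24 = 48 |
| 72 h | yes | 72 − 72 = 0 |
| 73 h | no | 0 |

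This part follows from the text alone and needs no assumption.

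**2. Effect on the safety rule (illustration)**

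Inputs:

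- *n* = 30, from Section 11.6.
- *p* = true risk of a device-related effect per participant. The protocol does not give it; 1%, 5% and 10% are assumed.
- *c* = share of those effects that are captured, either because they are apparent by the time of the call or because they are reported spontaneously or seen on the ward afterwards. The protocol does not give it; 100%, 90% and 50% are assumed. *c* = 100% means that the early call does no harm.

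Treating participants as independent, with at most one effect each:

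P(no effect detected) = (1 − *p* × *c*)^30

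For example, at *p* = 0.05:

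- *c* = 1: 0.95^30 = 0.215
- *c* = 0.9: 0.955^30 = 0.251
- *c* = 0.5: 0.975^30 = 0.468

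| Assumed risk *p* | *c* = 100% | *c* = 90% | *c* = 50% |
|---|---|---|---|
| 1% | 0.740 | 0.762 | 0.860 |
| 5% | 0.215 | 0.251 | 0.468 |
| 10% | 0.042 | 0.059 | 0.215 |

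Each entry is the chance that the study passes its safety rule. In every row it rises as capture falls. With 90% capture the rise is about 2 to 4 percentage points. With 50% capture it is 12 points at 1% risk, 25 at 5% and 17 at 10%.

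**The case against.** The best reply is that the schedule does give a time. The footnote hangs on a column headed 72 hours, it deals mainly with the mode of contact, and Section 10 makes adherence to the schedule essential. Read together, head, footnote and Section 10.3.2 could describe one end-of-study contact at a nominal 72 hours. The visible edit in Section 8.1, which strikes out 18–24 hours, also moves the limit later. This does not settle the matter. The footnote is attached to the head and relaxes it, Section 8.1 repeats the relaxation, and neither names an earliest time.

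The second reply concerns consequence, and much of it stands.

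- Collection is continuous, questioning is the preferred method rather than the only one, and later reports can still be recorded. What remains exposed is mainly late effects that discharged patients or outpatients do not volunteer.
- Only device-related effects count under Section 11.1.1. The likeliest delayed complaints may not count, because Section 10.3.4 lists them as procedure-related: "Commonly experienced events from an Echocardiogram include potential bruising, discomfort, focused pressure from the probe".
- Exposure is one scan of 30 to 60 minutes, with a sonographer at the bedside, a pressure limiter and emergency stops. The protocol's own example of a device-related event, a rib fractured by the arm, arises during the scan.
- The values of *p* and *c* are assumed. Capture of 50% would mean that half of all device-related effects in the cohort go unrecorded, and nothing in the protocol points to that.

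These points limit the size of the problem. They do not remove the mismatch: the protocol itself chose 72 hours as the period to watch, and its follow-up rule does not ensure that participants are asked about all of it.

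**Conclusion.** The concern holds. As written, the one scheduled safety contact can take place well before the adverse event window closes, and the rule forbids the slightly later call that would cover the whole window. The gap is in active questioning, not in formal collection, and it bears on the decision only through device-related effects that appear after the call and are not otherwise reported.

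The direction is certain: any such loss favours a pass. The size is not known, because it depends on the risk and onset of device-related effects, which the protocol does not give. It is near nil if effects show during or soon after the scan, and the probabilities in the working only illustrate what could happen otherwise. Confidence that this matters in practice is medium. It should be changed because the correction is cheap and safety is a primary objective.

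**What to change.** - In footnote 1 and Section 8.1, set the contact at or shortly after 72 hours, for example between 72 and 96 hours, with the questions covering the first 72 hours after the scan. This agrees with the column head in Section 4.
- In Section 10.3.2, keep the 72-hour collection window but drop the equation of 72 hours with the end of the study. Define the end of study as the follow-up contact.
- Record the date and time of the contact on the case report form, so that coverage of the window can be shown for each participant.

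The cost is wording in three places and one recorded time. The drawback is less freedom in timing the calls, mainly for outpatients and discharged patients.

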### 10.2 RUAT ECHO Scanning

Only trained and competent sonographers (see Section 6) will undertake RUAT ECHO. Sonographers will perform RUAT ECHO according to their training and the RUAT ECHO User Instructions.

	QMS Template	Doc ID: RMI-ROBOTECHO-CIP-002 Ver No: V2.0
	Clinical Investigation Protocol	

The RUAT Echo will be performed with a cardiac sonographer in the examination room at a sonographer remote workstation but not at the bedside (*'Performing Sonographer'*). A second sonographer (*'Observing Sonographer'*) shall be at the bedside and supervise the procedure. The *Performing Sonographer* must not have been involved in the participant's initial clinical assessment.

The RUAT system is connected via ethernet cable to the sonographer remote workstation and a wired gaming controller is used to operate the robotic system.

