**Figure 1: Scanning procedures**

	QMS Template	Doc ID: RMI-ROBOTECHO-CIP-002 Ver No: V2.0
	Clinical Investigation Protocol	

Cardiac sonographers will perform the RUAT Echo for up to 30 (total) recruited study participants. Although remotely performed in terms of the sonographer not holding the ultrasound probe in-hand (RUAT Echo exams), the *Performing Sonographer* will be physically co-located within the same room but not at the bedside of the study participant. This will provide patient and safety support for the procedure. The *Observing Sonographer* shall be at the bedside to supervise and verify that the RUAT performs as intended.

**Results of RUAT-performed echocardiograms will not be used for clinical treatment since treatment decisions would have already been made from the initial (manual) echocardiogram as the standard of care.**

The RUAT echocardiograms are only used to determine whether the images are of sufficient clinical quality to be reported on. In this regard 'clinical quality' refers to the images being classified as reportable by the sonographer.

At the end of the scan each study participant shall complete a RUAT experience survey.

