## 10.2.1 Evaluation

### 10.2.1.1 Functional verification of RUAT ECHO

The *Observing Sonographer* will complete a functional verification checklist (see APPENDIX 1 - Functional Verification ) to verify that the RUAT echo was performed as intended (as described in the Instruction Manual).

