### 10.2.1.2 Participant Experience Survey

Study participants' feedback on their experience from start to end of the RUAT echo will be collected via a feedback survey delivered to the participant by the *Observing Sonographer* or *health practitioner observer* at the completion of the RUAT echo. Data will be collected on the ability to interact with the *Performing Sonographer*, probe pressure and their perceptions on the movement of the robotic arm with invitation for open commentary and to express a preference for the manual versus robotic RUAT method (see

	QMS Template	Doc ID: RMI-ROBOTECHO-CIP-002 Ver No: V2.0
	Clinical Investigation Protocol	

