## 23.2 APPENDIX 2 – Participant Experience Survey

### Study Title:

Safety and useability of a novel robot-assisted echocardiographic examination – The RUAT ECHO Study – Medical Device Clinical Trial

**Principal Investigator:** [name]

Director of Cardiology and Senior Staff Cardiologist,

Cardiology, Royal Brisbane and Women’s Hospital

[[contact]](mailto:[contact])

**Study Coordinator:** [name]

Research Fellow, Research Manager, Program Manager,

Cardiology, Royal Brisbane and Women’s Hospital

[[contact]](mailto:[contact])

This survey has been provided to you as you have consented to participate in the **RUAT (ROBOT) ECHO study** and have undergone a robot cardiac ultrasound (also known as echocardiogram or ‘echo’). The following statements for you to provide are to investigate patient experiences regarding the RUAT echo procedure.

*Questions to be asked by research team (not the operating sonographer) to the patient.*

Thank you for agreeing to participate in this study. Please respond to the questions below on a 10-point scale of your level of comfort with the procedure.

1. Were you comfortable (and lacking concern) with the speed of the automatic movements when the probe was not on your chest?									
On a scale of 1 to 10 with 1 being extremely uncomfortable and 10 being extremely comfortable where does your experience sit on this scale?									
1	2	3	4	5	6	7	8	9	10
2. When the sonographer was actively adjusting the probe on your chest, did you feel safe?									
On a scale of 1 to 10 with 1 feeling extremely unsafe and 10 feeling extremely safe where does your experience sit on this scale?									
1	2	3	4	5	6	7	8	9	10

3. Were you comfortable with the pressure applied by the robot to the chest?									
On a scale of 1 to 10 with 1 being extremely uncomfortable and 10 being extremely comfortable where does your experience sit on this scale?									
1	2	3	4	5	6	7	8	9	10
4. Could you clearly see the video of the sonographer?									
On a scale of 1 to 10 with 1 being unable to see the video at all and 10 being able to clearly see the video unobstructed where does your experience sit on this scale?									
1	2	3	4	5	6	7	8	9	10

5. Do you wish to receive by email a layperson summary of the clinical trial results?"

*If yes, you understand that you are consenting to be contacted via email for the sole purpose of providing study results. Your information will not be used for any other purpose.*

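### The survey instructions in Section 4, Section 10.2.1.2 and Appendix 2 do not match, and all three leave room for the Observing Sonographer to help with ratings that feed a useability criterion

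*Protocol*

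**What the plan says.** Four places in the protocol describe how the participant experience survey is given.

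- Section 4, footnote 4: "Participant survey to be completed on paper after the RUAT Echo with the support of the observing sonographer".
- Section 10.2: "At the end of the scan each study participant shall complete a RUAT experience survey".
- Section 10.2.1.2: the survey is "delivered to the participant by the *Observing Sonographer* or *health practitioner observer* at the completion of the RUAT echo".
- Appendix 2, on the form itself: "Questions to be asked by research team (not the operating sonographer) to the patient".

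The Observing Sonographer has two other duties. In Section 10.2 this person "shall be at the bedside and supervise the procedure". In Section 10.2.1.1, "The *Observing Sonographer* will complete a functional verification checklist".

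The survey counts towards success. Table 2 lists participant experience as an endpoint under the primary useability objective, and Section 11.1.1 makes this one of three useability conditions: "At least 80% of participants report they are satisfied with undergoing RUAT Echo examination". The condition is judged on the average of the four rating items.

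**The concern.** The instructions differ on mode (a paper form filled in by the participant, or questions put by staff) and on the named administrator (the Observing Sonographer, that person or another observer, or the research team). Section 10 treats adherence to the Schedule of Assessments as essential and allows no waivers. Footnote 4 is part of that schedule, so a site that follows the instruction printed on the form may depart from it.

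The second issue is who may be present when the ratings are given. Three of the four items ask about comfort with the automatic movements, feeling safe while the probe was adjusted, and comfort with the pressure. A participant may be reluctant to give a low score with the help of someone who has just supervised the procedure at the bedside. Appendix 2 guards against this for the operating sonographer but not for the other member of the scanning pair. Section 10.3.3 asks for open, nonleading questioning about adverse events, and the protocol states nothing equivalent for the survey.

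At stake is one of the three useability conditions, judged on a simple proportion in about 30 people. Inconsistent collection cannot be undone at the analysis stage.

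**Working it through.** **Step 1. The passages side by side**

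| Place | Mode | Who is involved | Observing Sonographer |
|---|---|---|---|
| Section 4, footnote 4 | Paper form, with support | Observing Sonographer | Named |
| Section 10.2 | Participant completes | Not stated | Not excluded |
| Section 10.2.1.2 | Survey delivered | Observing Sonographer or health practitioner observer | Permitted |
| Appendix 2 | Questions asked by staff | Research team | Not excluded; only the operating sonographer is |

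The clearest difference is mode: footnote 4 against Appendix 2. The named administrator also varies. The health practitioner observer is not described elsewhere in the protocol text, and the research team is not defined.

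**Step 2. The plan's own figure**

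Section 11.6 gives an exact 95% interval for 80% of 30. It concerns image quality, but the count is the same, since 0.80 × 30 = 24. Clopper-Pearson for 24 of 30:

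- lower limit = 2.5% quantile of Beta(24, 7) = 61.43%
- upper limit = 97.5% quantile of Beta(25, 6) = 92.29%
- width = 30.85 points

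This agrees with the stated 61.4% to 92.3% and 30.9%. No figure in the protocol is in dispute.

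**Step 3. Sensitivity of the satisfaction criterion (illustration)**

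Inputs: n = 30 (Section 11.6), all assumed to respond; threshold 80% (Section 11.1.1), so 24 satisfied. If each participant reports being satisfied with probability p,

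P(pass) = Σ C(30, x) pˣ (1 − p)³⁰⁻ˣ, for x = 24 to 30.

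| p | P(at least 24 of 30) |
|---|---|
| 0.70 | 0.160 |
| 0.75 | 0.348 |
| 0.80 | 0.607 |
| 0.85 | 0.847 |

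The documents give no size for any courtesy effect, so the shifts below are assumptions.

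- True rate 70%, all shifted up 5 points: 0.16 becomes 0.35.
- True rate 70%, all shifted up 10 points: 0.16 becomes 0.61.
- True rate 70%, a random half shifted up 10 points: the average rate is 0.70 + 0.5 × 0.10 = 0.75, giving 0.35.
- True rate 75%, all shifted up 5 points: 0.35 becomes 0.61.

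These are chances of meeting the satisfaction criterion alone. Useability also requires each of checklist items 1 to 11, and item 12, to reach 80%.

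**The case against.** The strongest reply is that the instructions can be read together. The Observing Sonographer is not the operating sonographer and could count as research team, so one person could satisfy every version. The mode can be reconciled too: the form has printed 1 to 10 scales, and staff could read the items aloud while the participant marks the paper. Safeguards also exist. The operating sonographer may not ask the questions, and Section 20.1 keeps the co-investigator with a declared interest away from participants and from study data during the trial.

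Much of this stands. A reader might infer a flat contradiction about who gives the survey, but the wording does not go that far. A reader might also infer that Section 10.2.1.2 requires the Observing Sonographer's involvement. It speaks of delivery, not support, and allows another person. Nor did the Observing Sonographer run the scan: this person supervised while the Performing Sonographer operated the robot.

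Two further inferences are unsupported. Mixed modes make the data less consistent but have no inherent direction, so they cannot be said to favour a pass. And the pass probabilities do not measure bias. Section 11.1.1 gives no cut-off on the four-item average, so a shift in scores cannot be converted into percentage points of satisfied participants. The fourth item, on seeing the video, is largely factual and less exposed to courtesy.

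Last, coordinator or research staff also approach and inform participants (Section 10.1.1), so using them may reduce courtesy bias without removing it.

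The reply does not remove the point. The reading that reconciles all the versions is the one in which the bedside supervisor helps with the ratings.

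**Conclusion.** The point holds as an inconsistency of mode and administrator, together with a plausible but unquantified risk of courtesy bias in one of three useability conditions. The protocol does not show that bias will occur, and a reader should not conclude that it would produce a false useability pass, because the checklist and image-quality conditions must also be met.

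The size is illustrative only. It assumes 30 respondents, independent answers and shifts chosen for the example. On those terms, a shift of 5 to 10 points from a true rate of 70% would raise the chance of meeting the satisfaction criterion from 0.16 to between 0.35 and 0.61. With fewer respondents the figures would change. The case for acting is that the remedy is cheap, not that the effect is known to be large.

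**What to change.** State one mode and one administrator in Section 4 footnote 4, Section 10.2.1.2 and the instruction on the Appendix 2 form: the participant completes the paper form after the scan, and any help comes from the study coordinator or research staff already on the study, and from neither the Performing nor the Observing Sonographer. Remove the health practitioner observer from Section 10.2.1.2, and replace the Appendix 2 instruction that staff ask the questions.

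Returning the form sealed, or directly to the coordinator, is an optional extra.

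The cost is a wording change in three places, with no added participants or visits. The small downside is that a coordinator or member of the research staff must be available after each scan.

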### 11.1.4 Handling of Missing Data

Missing data will not be imputed.

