## 11.2 Analysis Sets

For the purposes of analysis, the following analysis sets are defined:

Participant Analysis Set	Description
Full analysis set (FAS)	All participants.
Safety analysis set (SAS)	All participants who are exposed to investigational medical device.

The full analysis set will be used to analyse endpoints related to the usability objectives and the safety analysis set will be used to analyse the endpoints and assessments related to safety.

All observed data will be used in the analysis.

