**13.2 Subject Withdrawals**

Subjects will be withdrawn from the study if:

- Their consent is withdrawn.
- In the investigator’s opinion, the subject’s clinical condition necessitates withdrawal for safety reasons.
- They are unable to tolerate RUAT echocardiogram procedure.

Subjects will be advised that they may voluntarily withdraw from the study at any time, for any reason and they are not obligated to reveal the reason to the sponsor, and it will not affect their medical care. However, in such cases, appropriate efforts will be made by the sponsor to determine the reason for voluntary withdrawal from the study.

Subjects will be informed that should they withdraw from the study they should remain in the care of an appropriately experienced physician until the physician deems further follow-up unnecessary.

A Study Completion Form will be completed for all patients who withdraw from the study.

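### The 80% satisfaction criterion can be read over completers only or over all participants, and the completers-only reading favours success when the scan is poorly tolerated

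*Protocol*

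**What the plan says.** **Survey timing.** Footnote 4 of the Schedule of Assessments (Protocol section 4) reads "Participant survey to be completed on paper after the RUAT Echo with the support of the observing sonographer". Section 10.2.1.2 has the survey delivered "at the completion of the RUAT echo". The introduction to the form in Appendix 2 addresses people who "have undergone a robot cardiac ultrasound". The scanning procedures in 10.2 are worded more broadly: "At the end of the scan each study participant shall complete a RUAT experience survey".

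**Early stops.** One of the withdrawal reasons in 13.2 is: "They are unable to tolerate RUAT echocardiogram procedure". Section 12 says participants will be told that they may stop if probe pressure becomes too uncomfortable.

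**Decision rule.** Section 11.1.1 requires: "At least 80% of participants report they are satisfied with undergoing RUAT Echo examination", judged on the average of four 10-point items.

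**Analysis rules.** Section 11.1.4: "Missing data will not be imputed". Section 11.2: "All observed data will be used in the analysis". Section 11.2 also assigns the useability endpoints to the full analysis set, defined as all participants. Section 11.1.3 marks intercurrent event strategies as not applicable, and 11.3.2.2 and 11.3.2.3 plan no sensitivity or supplementary analysis.

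**The concern.** A participant who stops because the robot scan is intolerable is the person most likely to score it badly: item 3 of the survey asks about comfort with the robot's pressure, which is the reason for stopping that section 12 foresees. If that person is withdrawn, gives no survey and is then left out because nothing is imputed, the missing value is caused by the outcome being measured. The percentage rises as tolerance falls.

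Stopping early is not a remote possibility in this line of devices. Table 1 of the Protocol reports that most proof-of-concept volunteers had some discomfort in the subcostal position. That was on an earlier robot, but the corresponding entry for the RUAT device is still under review.

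What is at stake is a stated pass/fail condition of a primary objective. If its denominator is open, the choice could be made after the data are seen.

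**Working it through.** **The plan's own figure.** The only precision figure is in 11.6 and concerns image quality, not satisfaction. The exact 95% interval for 24/30 is 61.4% to 92.3%, width 30.9 points, as stated. No figure is given for the satisfaction criterion.

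**Inputs.**
- Sample size 30 (11.6) and threshold 80% (11.1.1).
- Number k who stop for intolerance and give no survey: not in the Protocol. Assumed here as 1 to 4 of 30.
- Probability s that a completer is satisfied: not in the Protocol. Assumed as 0.85.
- Section 11.1.1 gives no score cut-off for being satisfied, so each respondent is simply treated as satisfied or not.

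**Step 1: where the verdicts part.** Over completers, m = 30 − k and the fewest satisfied needed is r = ceil(0.8 × m). Over all 30 it is 24.

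| k | m | r | r/m | r/30 | Verdict over all 30 at r |
|---|---|---|---|---|---|
| 1 | 29 | 24 | 82.8% | 80.0% | pass |
| 2 | 28 | 23 | 82.1% | 76.7% | fail |
| 3 | 27 | 22 | 81.5% | 73.3% | fail |
| 4 | 26 | 21 | 80.8% | 70.0% | fail |

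With k = 1 both readings need 24 satisfied, so the verdict cannot differ. With k = 2 they differ only at exactly 23 satisfied, with k = 3 at 22 or 23, and with k = 4 at 21, 22 or 23.

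**Step 2: chance of passing.** Let X be binomial(m, 0.85). Over completers the chance is P(X ≥ r). Over all 30, with those who stopped counted as not satisfied, it is P(X ≥ 24).

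| k | Over completers | Over all 30 |
|---|---|---|
| 1 | P(X ≥ 24 of 29) = 0.738 | 0.738 |
| 2 | P(X ≥ 23 of 28) = 0.765 | P(X ≥ 24 of 28) = 0.587 |
| 3 | P(X ≥ 22 of 27) = 0.790 | P(X ≥ 24 of 27) = 0.407 |
| 4 | P(X ≥ 21 of 26) = 0.815 | P(X ≥ 24 of 26) = 0.230 |

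**Step 3: the number stopping left random.** Let each participant stop with probability q. The completers-only chance is the sum over k of P(K = k) × P(X ≥ ceil(0.8(30 − k))), with K binomial(30, q). The all-participants chance is P(Y ≥ 24), with Y binomial(30, 0.85(1 − q)). The results are 0.78 against 0.65 at q = 5%, 0.78 against 0.42 at 10%, and 0.78 against 0.11 at 20%. The completers-only figure hardly moves as intolerance rises, so the rule would not register poor tolerance.

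**The case against.** The strongest reply is that the bias is not written down.

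- Footnote 4 says after the scan. It does not say only after a completed scan. The word completion appears in 10.2.1.2 and can be read as timing alone.
- Section 10.2 makes the survey universal, and a scan stopped early has also ended.
- Section 13.2 lists reasons for withdrawal but does not say that same-day assessments cease. A survey taken from someone who stopped would count as observed data.
- A criterion worded over participants, on a full analysis set of all participants, can be taken to keep non-responders in the denominator as people who did not report satisfaction. The ban on imputation sets no denominator.

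All of this stands. A reader might infer that the plan removes every intolerant participant from the percentage. The documents do not say so: exclusion is the likely result of combining the sections, not a stated rule.

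The size is also unknown. Section 13.1 expects all subjects to complete, section 12 limits probe pressure to about half of a human operator's maximum, and the earlier 78-person study was reported as safely performed (5.2). These points lower the likelihood of several stops. They do not settle which denominator applies if stops occur.

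Deferral to the SAP answers only part of this. Section 11 does leave technical detail to the SAP, but the Protocol itself fixes no imputation and no intercurrent event strategy, and a SAP cannot recover surveys that were never offered.

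**Conclusion.** The point holds as an unresolved conflict in a primary decision rule, with one of its two readings biased towards success. Sections 10.2.1.2, 11.1.3, 11.1.4, 11.2 and 13.2 together allow a completers-only percentage, while 10.2 and the definition of the full analysis set point to all participants.

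The size depends on an assumed number of intolerance stops. One stop in 30 is harmless. From two upwards the verdict can reverse, and with 85% of completers satisfied the chance of passing is 76% against 59% for two stops, 79% against 41% for three, and 82% against 23% for four. These figures illustrate what the open denominator could do. They do not predict the trial's result and do not show that bias will occur.

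The point concerns only the satisfaction criterion. It should be corrected before enrolment, because the survey timing cannot be repaired afterwards.

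**What to change.** 1. In 10.2.1.2 and footnote 4, in line with 10.2, state that the survey is offered whenever a started scan ends, for whatever reason. It remains voluntary, and the withdrawal rules in 13.2 are unchanged.
2. In 11.1.1, define the denominator of the satisfaction criterion as all participants in whom a RUAT Echo was started, and count those who stopped for intolerance as not satisfied.
3. In 11.1.3, name stopping for intolerance as an intercurrent event handled in this way. In 11.1.4 and 11.2, state the rule as the exception to no imputation, to use of observed data and to the full analysis set. Without these edits, step 2 would create new contradictions.
4. Report the observed-case percentage beside the main result, including any scores given by those who stopped.
5. Show surveys missing for other reasons, such as a lost form or a device fault, separately, with a worst-case count as a sensitivity result. Scoring these as dissatisfaction in the main rule would be hard to defend. Amend 11.3.2.2 accordingly, since it now plans no sensitivity analysis.

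The cost is wording in these sections, with no extra visit or new data source. The reported satisfaction rate may be slightly lower.
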